The primary analysis of the primary outcome implicitly adopts a last-observation-carried-forward approach. Multiple imputation will be used for the primary analysis of the secondary outcome and may also be used for other outcomes, as described in the Statistical Analysis Plan. Because the sample size is modest, it may not be feasible to use complex multiple imputation models, but candidate variables for the imputation of missing values for the secondary outcome will include variables such as assigned treatment arm and wound area measurements from other study visits. As sensitivity analyses, the analyses of the primary and secondary outcomes will be repeated twice, first replacing each missing outcome with the lowest observed outcome at that timepoint from among subjects in the same assigned treatment arm, and then again replacing each missing outcome with the highest observed outcome at that timepoint from among subjects in the same assigned arm.

A number of additional prespecified exploratory analyses will be conducted. Although the overall sample size is modest, subgroup analyses were requested by the FDA and will be conducted for the primary and secondary outcomes using subgroups defined by the following variables: sex; race; ethnicity; diagnosis of diabetes mellitus or a screening hemoglobin A1C greater than or equal to 6.5; use of immunosuppressive medications; presence/absence of known malignancy other than non-metastatic basal or squamous cell carcinoma; nutritional status as defined by albumin levels; presence/absence of blood coagulation conditions defined by PT/INR and PTT levels; presence/absence of venous vascular disease affecting the wound area; presence/absence of arterial vascular disease affecting the wound area; Visit

1 oxygen saturation  $<90\%$  or  $\geq 90\%$ ; and concomitant anticoagulation medication or lack thereof. The details of the subgroup analysis will be available in the Statistical Analysis Plan (SAP).

Finally, although some additional collected data elements may influence the response, the primary and secondary analyses will not adjust for these other characteristics because the modest sample size makes such adjustments impractical. The randomization procedure will be relied upon to avoid favoring either treatment arm in the safety and efficacy comparisons. Exploratory analyses may be conducted to attempt to adjust for one or more additional variables.

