5.2 Methods for Withdrawals, Missing Data, and Outliers

The applicability of some measures will depend on whether or not the wound is (or has previously) closed. Values that are not observed because they are not applicable will be excluded from the pertinent analyses, rather than regarded as missing. Values that are not directly obtained but are implied by other measurements will use the implied value.

Multiple imputation (MI) will be applied for analyses of the secondary outcome. Using MI leverages partial information and attempts to reduce bias in final inferences that could result from a naive complete-case analysis. A minimum of ten data sets will be generated. Chained equations will be used along with variable selection; for imputing missing values for a given variable, the input variables will be limited to those that increase the R^2 value by at least 0.01. If feasible, MI will be conducted separately within each treatment arm. The pool of variables for the imputation process includes: wound area per the imaging software at Visits 1, 2, 3, 4, and 5; treatment arm if infeasible to impute by treatment arm; and indicators for comorbidities. The following comorbidities will be considered: diabetes, peripheral vascular disease, and immunosuppression. Imputation will exclude individuals

who were not randomized.

Visit measurements obtained outside the permissible window may or may not be used in the imputation model. We will determine the closest visit number to assign the out-of-window visit per the protocol's timing for follow-up visits. The out-of-window measurement will be used for the determined visit number in the case that the visit number does not already have a valid measurement (and if there are multiple out-of-window candidate measurements, the one closest to the protocol timing will be used). Otherwise, the out-of-window measurement will be ignored.

Multiple imputation may also be used for exploratory outcomes, as appropriate.

We do not plan to use different methods for missing data due to withdrawal compared with data missing for other reasons.

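### If imputation by arm is judged infeasible, the 0.01 R-squared rule in SAP 5.2 can leave treatment arm out of the imputation model for the secondary outcome

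*SAP*

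**What the plan says.** SAP 5.2 prescribes multiple imputation by chained equations for the secondary outcome, percent reduction in wound area from Visit 2 to Visit 5. The preferred route is stratified: "If feasible, MI will be conducted separately within each treatment arm". Predictors are selected separately for each variable to be imputed: "the input variables will be limited to those that increase the R^2 value by at least 0.01". The pool contains "wound area per the imaging software at Visits 1, 2, 3, 4, and 5", three comorbidity indicators (diabetes, peripheral vascular disease, immunosuppression) and, in the fallback, "treatment arm if infeasible to impute by treatment arm".

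Protocol section 8 (Statistical Method) also gives arm only candidate status: "candidate variables for the imputation of missing values for the secondary outcome will include variables such as assigned treatment arm". It adds a caution: "Because the sample size is modest, it may not be feasible to use complex multiple imputation models". Neither document defines when by-arm imputation becomes infeasible, gives an expected missing-data rate, or says that arm is retained whatever it adds to R-squared.

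**The concern.** An imputation model should contain the variable whose effect will be tested on the completed data. If arm is left out, missing Visit 5 areas in both arms are drawn from one regression that ignores treatment. Imputed subjects then carry only the part of the treatment effect that passes through their other observed wound areas, and the between-arm difference shrinks.

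Arm is a likely candidate to fail the filter because it competes with wound areas from other visits. Those areas may explain most of the variance in Visit 5 area, which leaves little for arm to add even when pAF works as SAP section 8 supposes. Whether arm stays would then depend on the sample, not on a prespecified choice.

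At stake is the only formal efficacy test outside the exploratory analyses (SAP 5.3), which has about 54% power even with complete data.

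**Working it through.** **Inputs from the documents.** 30 subjects per arm; closure probability 0.2 (SOC) and 0.5 (pAF); remaining reductions uniform on 0-100% (SAP section 8); two-sided 0.05 (SAP 5.3 and 7.3); at least ten imputations (SAP 5.2).

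**Step 1: the plan's own figure.** Simulating 20,000 trials from these inputs with the two-sided Wilcoxon test gives power of 54.6-54.8%, against the stated figure of about 54%. The Welch t-test gives 42.5%.

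**Step 2: the effect implied by SAP section 8.**
- Means: pAF 0.5 × 100 + 0.5 × 50 = 75; SOC 0.2 × 100 + 0.8 × 50 = 60; difference 15.
- Variances, with E[U²] = 10,000/3: pAF 0.5 × 10,000 + 0.5 × 3,333.3 − 75² = 1,041.7; SOC 0.2 × 10,000 + 0.8 × 3,333.3 − 60² = 1,066.7. Average 1,054.2, SD about 32.5.
- Population R-squared of arm alone: 7.5² / (7.5² + 1,054.2) = 56.25 / 1,110.4 = 0.051.

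**Step 3: arm as sole predictor.** Sample R-squared falls below 0.01 when |t| < √(0.01 × df / 0.99), with df = n − 2. At n = 60 the cut-off is 0.765. With noncentrality (15/32.5) × √60 / 2 = 1.79, the probability is 15%. At n = 42 (30% missing) the cut-off is 0.636, the noncentrality is 1.50 and the probability is 18%. Standing alone, arm would usually pass.

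**Step 4: arm competing with the wound areas.** This step needs assumptions that the documents do not supply. In the twelve settings tabulated:
- Visit 2 area is uniform on 5-75 cm².
- Percent reduction is 0.35 (Visit 3) and 0.6 (Visit 4) times the Visit 5 reduction, plus normal noise with SD 10 or 30 points.
- Comorbidities occur at 40%, 30% and 15% and are unrelated to outcome.
- Data are missing completely at random, either at Visit 5 only or at Visits 3-5.

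Each setting used 800 trials, forward selection at an R-squared increment of 0.01, ten Bayesian linear imputations run sequentially, imputed areas truncated at 0 and at twice the Visit 2 area, a comparison of means and Rubin's rules. Estimates are pAF minus SOC in points.

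| Missing visits | Noise SD | Missing | Arm dropped, Visit 5 model | 0.01 rule | Arm kept | Rule minus kept | By arm |
|---|---|---|---|---|---|---|---|
| 3-5 | 10 | 10% | 92% | 13.98 | 14.62 | −0.63 | 14.37 |
| 3-5 | 10 | 20% | 92% | 13.01 | 14.29 | −1.28 | 13.82 |
| 3-5 | 10 | 30% | 89% | 13.24 | 15.14 | −1.90 | 13.98 |
| 3-5 | 30 | 10% | 42% | 15.03 | 15.22 | −0.20 | 14.98 |
| 3-5 | 30 | 20% | 42% | 14.79 | 15.14 | −0.35 | 14.40 |
| 3-5 | 30 | 30% | 45% | 13.69 | 14.27 | −0.58 | 13.45 |
| 5 only | 10 | 10% | 92% | 14.27 | 14.45 | −0.18 | 14.39 |
| 5 only | 10 | 20% | 88% | 14.63 | 14.91 | −0.28 | 14.85 |
| 5 only | 10 | 30% | 89% | 13.92 | 14.38 | −0.46 | 14.13 |
| 5 only | 30 | 10% | 41% | 15.04 | 15.12 | −0.08 | 15.04 |
| 5 only | 30 | 20% | 43% | 14.34 | 14.65 | −0.31 | 14.19 |
| 5 only | 30 | 30% | 45% | 14.72 | 15.06 | −0.34 | 14.57 |

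Simulation standard errors of the paired differences are 0.03 to 0.13, so −0.08 (standard error 0.05) is within noise.

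**Step 5: wider range.** Across 30 settings in all, including log-normal wound sizes and imputation on the percentage scale, the rule gave the lower estimate every time, by 0.1 to 1.9 points. With Visits 3-5 missing, arm was absent from all three imputation models in 7-55% of trials. Rejection rates were usually 0-4 points lower under the rule and at most about 6 (24.6% to 18.5%, 20% missing from Visit 3 on). A second simulation of the same SAP effect dropped arm in 38-55% of trials and lowered the estimate by about 0.15-0.35 points.

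**The case against.** The strongest reply is that this concerns a fallback. By-arm imputation comes first, the pool is small (five areas and three comorbidities), and the protocol's caution is about complex models. The authors may also have intended arm to stay once it enters the pool. All of that is fair, but feasibility is undefined, about 30 subjects per arm before losses is not many for chained equations, and the text as written does not protect arm.

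The size is also open to challenge. Later-visit areas carry part of any treatment effect, and arm tends to be dropped when its sample contribution is small; both limit the loss. By-arm imputation, which cannot omit arm, itself came out 0.06 to 1.16 points below the arm-kept model in the table, and no higher than the 0.01 rule when noise was 30 points. The loss is therefore of the same order as the differences between acceptable methods. SAP 7.3.1 adds two sensitivity analyses that fill missing values within the assigned arm and do not use the filter.

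Two stronger readings are tempting. A reader might infer that arm is always lost. In simulations where it was never included, with Visits 3-5 missing, the estimate fell to about 10-13.8 points, but SAP 5.2 prescribes a sample-dependent rule, not exclusion. A reader might also infer that the filter admits an irrelevant variable about half the time. That holds for a sole predictor (0.45 at n = 60). The rule concerns the increase in R-squared: with three wound areas already explaining 50-90% of the variance, the pass probability at n = 60 is 0.29 down to 0.02.

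**Conclusion.** The gap in the text is real and the effect is modest. In the fallback, SAP 5.2 lets the sample decide whether the tested variable is in the imputation model. Under the SAP section 8 effect, arm is dropped from the Visit 5 model in roughly 40-90% of simulated trials, and the estimate is about 0.1 to 1.9 points lower than with arm kept. The largest loss is 1.90 of 15.14, or 12.5%, at 30% missing from Visit 3 on with closely correlated visits. With only Visit 5 missing, the loss stays at or below about 0.5 points.

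The drop rate rests on assumed visit correlations, wound sizes and missingness, and data missing completely at random. The documents do not support calling omission of arm typical, or the bias large. The point concerns the secondary endpoint only and arises only when imputation is not done by arm. It is a low-severity clarification, worth making because the direction was the same in every setting and works against detecting a pAF effect.

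**What to change.** Add one sentence to SAP 5.2: when imputation is not carried out separately by arm, treatment arm is kept in every imputation model, and the 0.01 R-squared rule applies only to the other candidates. It would help to state as well when by-arm imputation counts as infeasible, for example as a minimum number of observed subjects per arm, so that the route does not depend on judgment after the data are seen. Forcing in Visit 2 area is optional; the calculations above do not bear on it.

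The cost is a sentence or two of SAP text. The endpoint, the test, the sample size and data collection are unchanged.

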5.3 Multiple Comparisons and Multiplicity

There is one primary endpoint (occurrence of post-randomization study-related SAEs on or before Visit 5), which is not intended to be tested between arms. Instead, descriptive summaries and confidence intervals will be constructed by study arm. There is one secondary endpoint (percent reduction in wound area at Visit 5 compared to Visit 2), which will be tested at $\alpha = 0.05$. The additional analyses are regarded as exploratory and therefore no adjustments are indicated for the multiplicity of testing; each will use $\alpha = 0.05$.

5.4 Planned Subgroups, Interactions, and Covariates

The primary and secondary outcomes will be analyzed within the following subgroups; these analyses will be considered exploratory even though they are prespecified. Determination of subgroups is per Visit 1 assessment, unless stated otherwise.

- Sex (male, female)
- Race (white, non-white)
- Ethnicity (Latinx, non-Latinx)
- Diabetes Mellitus or high A1C (diagnosis or A1C ≥ 6.5 , no diagnosis and A1C < 6.5)
- Use of immunosuppressive medications (yes, no)
- Known malignancy other than non-metastatic basal or squamous cell carcinoma (yes, no)
- Nutritional status (albumin level < 3.0 , ≥ 3.0)

- Blood coagulation conditions ($PT/INR > 1.0$ or $PTT > 15$, $PT/INR \leq 1.0$ and $PTT \leq 15$)
- Venous vascular disease affecting the wound area (yes, no)
- Arterial vascular disease affecting the wound area (yes, no)
- Visit 1 oxygen saturation ($< 90\%$, $\geq 90\%$)
- Concomitant anticoagulation medication (yes, no)
- Injury type/disease etiology: (ulcer, trauma, post-surgical non-healing wound, other)

For the subgroup analyses, if a subject's subgroup cannot be ascertained or is not compatible with any of the stated options, the individual will be excluded from the analysis of that subgroup.

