7.5 Technical Approaches for Subgroup Analyses

For each subgroup, the primary outcome and secondary outcome will be analyzed in separate models with a main effect for subgroup level, a main effect for treatment arm, and the subgroup \times treatment interaction effect. The interaction effects are the targets for the subgroup analyses. For the primary outcome, exact logistic regression or (ordinary) logistic regression will be used, as appropriate. For the secondary outcome, quantile regression for the median or linear regression for the mean, as appropriate, will be used.

Because of the modest sample size and large number of subgroups, the exploratory nature of these analyses is especially important to emphasize. If any subgroup analyses are not feasible to conduct (e.g., no participants have the primary outcome), the infeasible subgroup analyses may be omitted.

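### The coagulation subgroup in SAP 5.4 has cut-offs without units or reference range; if PTT is in seconds on a conventional scale, its reference level is expected to be empty

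*SAP*

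**What the plan says.** The protocol (section 8, Statistical Method) lists, among the subgroup variables requested by the FDA, "presence/absence of blood coagulation conditions defined by PT/INR and PTT levels". It gives no cut-offs there. The numbers come only from SAP 5.4, which defines the present level by "Blood coagulation conditions ($PT/INR > 1.0$ or $PTT > 15" and the reference level as PT/INR at or below 1.0 together with PTT at or below 15. Neither document gives a unit, a laboratory reference range, a rationale or an expected split.

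On timing, SAP 5.4 says "Determination of subgroups is per Visit 1 assessment, unless stated otherwise". PT/INR and PTT are both on the protocol's Visit 1 laboratory list.

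SAP 7.5 fits a model with "a main effect for subgroup level, a main effect for treatment arm, and the subgroup \times treatment interaction effect" and adds that "The interaction effects are the targets for the subgroup analyses". On status, SAP 5.4 says "these analyses will be considered exploratory even though they are prespecified". SAP 7.5 also provides that "the infeasible subgroup analyses may be omitted".

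**The concern.** The protocol asks for a contrast between subjects with and without a coagulation condition. The SAP rule joins two cut-offs with *or* for the present level, and therefore with *and* for the reference level. If either cut-off lies below nearly all observed values, the reference level empties whatever the other cut-off does. A PTT cut-off of 15 looks like that if the unit is seconds.

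An interaction needs reference-level subjects in both arms. Without them, a subgroup analysis that the protocol says the FDA requested would be lost because of its definition rather than because of the data. With one or two stray reference subjects per arm the model would run but say very little, and under SAP 5.3 it would still be tested at 0.05 without adjustment.

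The label PT/INR also merges two scales. Prothrombin time is a time and INR is a ratio, so one cut-off of 1.0 cannot serve both.

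**Working it through.** **Inputs from the documents.** 30 subjects per arm and 60 in total (SAP 8); the two-level rule (SAP 5.4); the model with interaction (SAP 7.5).

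**Input not in the documents.** The distribution of PTT. It is assumed normal, in seconds, over a range of means *m* and SDs *s*.

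**Plan's own figures.** No split is stated for this subgroup, so there is none to reproduce. The general design figures do reproduce. The Wilcoxon power is 54.1% over 20,000 simulated trials (stated: about 54%). The exact lower bounds for 0 to 3 events in 30 are 90.5, 85.1, 80.5 and 76.1% (stated: 90, 85, 80 and 76%).

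**Step 1, bound.** Let *q* be the share in the reference level. Since both conditions are required, *q* ≤ P(PTT ≤ 15).

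**Step 2, size of the bound.** P(PTT ≤ 15) = Φ((15 − m)/s). The expected number is 60 × P, and the chance of no reference subject is (1 − P)^60.

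| m / s | (15 − m)/s | P(PTT ≤ 15) | Expected of 60 | Chance of none |
|---|---|---|---|---|
| 25 / 3 | −3.33 | 0.043% | 0.026 | 97.5% |
| 30 / 4 | −3.75 | 0.009% | 0.005 | 99.5% |
| 30 / 5 | −3.00 | 0.135% | 0.081 | 92.2% |
| 32 / 6 | −2.83 | 0.230% | 0.138 | 87.1% |
| 35 / 5 | −4.00 | 0.003% | 0.002 | 99.8% |
| 20 / 3 | −1.67 | 4.8% | 2.9 | 5.3% |
| 12 / 1.5 | +2.00 | 97.7% | 58.6 | about 0 |

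The first five rows cover means of 25 to 35. The last two show where the conclusion weakens and where it fails.

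**Step 3, estimability.** The design matrix has four columns: intercept, subgroup, arm and interaction.
- No reference subjects: rank 2. Neither the subgroup effect nor the interaction is estimable.
- Reference subjects in one arm only: rank 3. The interaction is still not estimable.
- At least one in each arm: rank 4. The interaction is estimable for the secondary outcome.

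The chance that at least one arm has no reference subject is 1 − (1 − (1 − q)^30)².
- q = 0.23% (the 32/6 row): 0.9977^30 = 0.933, so 1 − 0.067² = 99.6%.
- q = 1%: 93%. q = 2%: 79%. q = 10%: 8%.
- q = 4.8% (the 20/3 row): 0.952^30 = 0.230, so 1 − 0.770² = 41%. This ignores the INR condition, which can only lower q.

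**Step 4, precision when it is estimable.** With *r* reference subjects per arm, the interaction SE in outcome SDs is √(2(1/r + 1/(30 − r))).
- r = 1: √(2(1 + 1/29)) = 1.44.
- r = 2: 1.04.
- r = 15 (even split): √(4/15) = 0.52.

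One reference subject per arm therefore gives an SE 1.44/0.52 = 2.8 times that of an even split.

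**Step 5, the INR term alone.** Assume INR in normal subjects is centred on 1.0 with SD 0.05 to 0.10. Then 50% of them exceed 1.0. If INR is reported to one decimal, a recorded value above 1.0 means a true value above about 1.05, which gives 16% (SD 0.05), 27% (SD 0.08) or 31% (SD 0.10). Both levels stay populated, but a sizeable share of normal subjects is labelled as having a condition. If the term is instead read as prothrombin time in seconds, a cut-off of 1.0 would capture everyone.

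**The case against.** A reader might infer that essentially every subject is bound to land in the present level and that the interaction simply cannot be estimated. The documents do not support that.

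- They give no PTT unit or range. To assume that every PTT lies between 20 and 40 and conclude that all 60 exceed 15 is circular. The result depends on the assumed distribution: at 20/3 about 3 reference subjects are expected, and if PTT typically lay at or below 15 the problem would vanish.
- One reference subject per arm is enough for the secondary-outcome interaction to be estimable, though poorly.
- On the INR reading, the PT/INR term would not empty the level. Its fault is labelling.

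The consequence is also contained. This is one of 13 exploratory subgroups, and SAP 7.5 stresses their exploratory nature and allows infeasible ones to be dropped. For the primary outcome the interaction may be infeasible whatever the cut-off, if few or no related SAEs occur. SAP 5.5 defers key derived-variable definitions to a separate specifications document, which might settle the units. Nothing shows that the FDA asked for particular thresholds.

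These points stand and set the severity. They do not remove the defect. The omission clause would drop a requested analysis because of how it was defined. Dual programming (SAP 5.5 and 5.6) would reproduce the same rule twice. A specifications document that stated units would still leave the SAP cut-offs in place.

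**Conclusion.** The concern holds in conditional form. If PTT is in seconds with a mean of about 25 to 35, the reference level is expected to hold at most about 0.14 of 60 subjects, with an 87% to over 99% chance of none. The interaction is then expected to be non-estimable, or nearly uninformative if a stray reference subject falls in each arm. At an assumed 20/3 the failure is less certain: about 3 reference subjects, and about a 41% chance that at least one arm has none.

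The PTT term drives this result. The INR cut-off at 1.0 adds a labelling fault under its own assumption, and the merged PT/INR label needs correcting on any assumption.

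The severity is minor. The analysis is exploratory, and the primary analysis, the secondary analysis and the sample size are untouched.

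**What to change.** Amend the coagulation line in SAP 5.4 before arms are compared:

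- Name the first quantity as INR and state the PTT units.
- Replace both cut-offs with the testing laboratory's upper limits of normal: either value above its limit, against both at or below.
- Count the two levels on data pooled across arms. If one level is too sparse, report the subgroup descriptively under the infeasibility provision of SAP 7.5.

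The cost is one SAP line. The Visit 1 laboratory values are already collected, so no new data are needed. The downside is that the present level may become the sparse one, since nothing in the documents shows how many subjects would exceed the laboratory's limits. A change made before arms are compared keeps the subgroup prespecified. A later change would have to be reported as post hoc under SAP 1.2.
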